13.4 Statistical Analysis for Translational Studies

Due to the limited sample size in this study, the proposed translational studies are considered exploratory and hypothesis generating. We plan to estimate the effects of efatutazone treatment on the following translational endpoints:

- 1) PPAR γ and RXR tumor expression from archived patient tumor samples
- 2) PPAR γ -regulated markers of adipocyte differentiation.
- 3) PPAR γ -regulated cell cycle proteins

We will also correlate the tumor marker data with clinical endpoints (i.e. response, PFS, OS, and adverse events). Statistical and graphical techniques will be used to explore these relationships. For time-to-event endpoints, we will use Cox proportional hazards models, and for response/toxicity we will use Logistic regression models. In addition, we will use the Fisher's exact tests to test the association between categorical marker data and response/toxicity.

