13.2 Primary Endpoint and Study Design

The primary endpoint for this study will assess the confirmed response rate (by RECIST 1.1) of efatutazone in patients with advanced, unresectable, or metastatic myxoid liposarcoma who have received at least one prior systemic therapy. Any confirmed response that occurs during the first 8 cycles of treatment will count as a success (24 weeks). Per RECIST 1.1, responses need to be confirmed (2 consecutive responses at least 4 weeks apart) to count as a response (see Section 11). All eligible patients who are registered and start treatment will be evaluable for response. A Simon's optimal two-stage design will be utilized (see below). This design has 80% power to detect an improvement in the confirmed response rate from 5% to 20%, with a significance level of 0.10. See design details below:

Interim Analysis: Enroll 9 eligible patients (need 6 additional patients after design change to single arm trial). If at least 1 confirmed response is observed in the first 9 eligible patients, we will continue the study to a full accrual of 24 eligible patients. Otherwise, the study will be permanently closed due to lack of efficacy. The study will remain open during the interim analysis phase due to slow projected accrual rate and minimal expected toxicity.

Final Analysis: If the trial is a success during the interim analysis, we will enroll another 15 eligible patients (24 eligible total). If at least 3 confirmed responses are observed in the first 24 eligible patients (13%), the treatment will be considered worthy of further investigation. Otherwise, the study will be permanently closed due to lack of efficacy.

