13.5 Total Sample Size, Accrual Duration, and Anticipated Time to Study Completion

A maximum of 24 evaluable patients (21 new efatutazone treated patients + 3 already randomized previously) will be accrued onto this randomized phase II study unless the study is closed early for excessive toxicity or lack of efficacy. We anticipate accruing an additional 20% of patients to account for ineligibility, cancellation, major treatment violation, or other reasons. Therefore, maximum accrual is about 30 patients (up to 28 treated with efatutazone (25 new, 3 already enrolled) + 2 placebo treated patients (already enrolled from prior randomized study)). With an expected accrual rate of 1 patient per month, we anticipate that it will take about 3 years to reach full accrual. We anticipate that the study will take approximately 4 years to complete. This allows a 6-month follow-up for the final patient enrolled, along with data entry and analysis.

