13.9 Descriptive Factors

- Progression prior to starting treatment: Within 1 month vs. within 2-6 months
- Tumor characteristics:
 - RXR expression: high vs. low
- Number of prior lines of therapy: 1 vs. 2 or more
- Prior anthracycline: yes or no
- Prior trabectedin: yes or no

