14.0 CORRELATIVE STUDIES

There is one substudy within Alliance A091202. This correlative science study **must be offered to all patients** enrolled on Alliance A091202 (although patients may opt to not participate). This substudy does not require separate IRB approval. The substudy included within Alliance A091202 is:

Analysis of Cell Cycle Regulated Proteins and Markers of Differentiation, Alliance A091202-ST1

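### Marker–response models are planned as plain logistic regression with about 3 to 5 responders in at most 24 patients, so a high/low marker will quite often have no finite odds ratio

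*Combined protocol and SAP*

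**What the plan says.** Section 13.4 calls the translational work exploratory and hypothesis generating because the sample is small. It then plans to relate the tumour markers to response, PFS, OS and adverse events, with Cox models for the time-to-event endpoints. For the binary endpoints it says "for response/toxicity we will use Logistic regression models". It adds Fisher's exact tests for categorical markers against response and toxicity. It gives no penalised or exact form of the logistic model, no minimum number of responders, and no rule for separation or non-convergence.

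The amount of data follows from the design. Section 13.5 sets "A maximum of 24 evaluable patients". Section 13.2 continues past stage 1 "If at least 1 confirmed response is observed in the first 9 eligible patients" and requires at least 3 responses in 24 for success. The marker sample may be smaller still: Section 14.0 offers the substudy to everyone "although patients may opt to not participate".

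The coding of the markers in these models is left open. Section 13.9 lists "RXR expression: high vs. low" as a descriptive factor, without a cut-off and without a link to 13.4. Section 14.3.1 gives PPARγ and RXRα a score from 1 to 9 and also plans the product of their percentages of positive cells. The additional markers get a final score from 0 to 3.

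**The concern.** When every responder falls in one group of a two-level marker, the likelihood has no maximum at a finite log-odds ratio. Software then stops with an error, or returns a very large coefficient with a meaningless standard error. With 3 to 5 responders this is not a rare accident. It also tends to happen in the case the substudy hopes to see, where all responders are marker-high.

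Sections 2.3 and 14 make the search for predictive markers an explicit aim. What is at stake is whether the analysis can report an effect size with a usable interval, and whether the method is chosen beforehand or improvised after the table has been seen.

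**Working it through.** **Inputs from the documents.** Section 13.2: null rate 5%, target rate 20%, "improvement in the confirmed response rate from 5% to 20%, with a significance level of 0.10", 80% power, 9 then 24 patients, at least 1 then at least 3 responses. Section 13.5: at most 24 evaluable patients. **Assumptions.** Marker splits of 12/12 and 8/16, the true odds ratios, and the size of shift in a numeric score are not in the documents.

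**1. The plan's own figure.** P(success) = Σ over a ≥ 1 of Bin(a; 9, p) × P(Bin(15, p) ≥ 3 − a). This gives 0.0931 at p = 0.05 and 0.8047 at p = 0.20, so the stated significance level and power are reproduced. P(stop early at 5%) = 0.95^9 = 0.630.

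**2. Responders to expect.** The success threshold is 3 (3/24 = 12.5%). At the target rate, 0.20 × 24 = 4.8. Given that stage 1 is passed, the mean is 3.5 at 12.5% and 5.1 at 20%, and P(3 to 5 responders) is 0.63 and 0.54. At 5% the conditional mean is about 2.

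**3. Empty responder cell, null high/low marker.** With k responders and h marker-high patients, P = [C(h,k) + C(24−h,k)] / C(24,k).

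| k | 12/12 split | 8/16 split |
|---|---|---|
| 2 | (66+66)/276 = 0.48 | (28+120)/276 = 0.54 |
| 3 | (220+220)/2024 = 0.22 | (56+560)/2024 = 0.30 |
| 4 | (495+495)/10626 = 0.09 | (70+1820)/10626 = 0.18 |
| 5 | (792+792)/42504 = 0.04 | (56+4368)/42504 = 0.10 |

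**4. Averaged over trials that reach 24 patients.** Full accrual requires a response in the first 9, so each k is weighted by Bin(k; 24, p) × [1 − C(15,k)/C(24,k)] / [1 − (1−p)^9]. Results (12/12 to 8/16): 26–32% at p = 12.5%, 10–16% at p = 20%, 60–64% at p = 5%. Restricted to trials with at least 3 responses: 12–19% at 12.5% and 6–12% at 20%.

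**5. Predictive high/low marker.** For response rates of 35% and 5% in groups of 12: 0.65^12 = 0.0057, 0.95^12 = 0.540, and 1 − (1 − 0.0057)(1 − 0.540) = 0.54. This is not conditioned on stage 1. With a fixed number of responders (3 / 4 / 5), a 12/12 split and a true odds ratio of 10, it is 0.72 / 0.61 / 0.51; with an odds ratio of 5, 0.54 / 0.41 / 0.30.

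**6. Other codings** (3 / 4 / 5 responders). A null four-level factor with 6 patients per level has at least one level without responders in 1.00 / 0.88 / 0.70. A continuous score entered as one numeric term separates in at most 0.001 under the null, 0.02 / 0.01 / 0.005 for a 1 SD shift, 0.13 / 0.08 / 0.06 for a 1.73 SD shift (AUC about 0.89), and 0.63 / 0.56 / 0.51 for a 3 SD shift.

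**7. What each method reports** (12/12 split, all responders marker-high).

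| Table | Maximum likelihood | Firth OR (95% profile interval) | Fisher two-sided p |
|---|---|---|---|
| 3/12 vs 0/12 | log-OR 26, SE above 200,000 | 9.2 (0.76 to 1297) | 0.22 |
| 4/12 vs 0/12 | log-OR 31, SE above 1,700,000 | 13.2 (1.17 to 1843) | 0.093 |
| 5/12 vs 0/12 | singular matrix | 18.3 (1.69 to 2539) | 0.037 |

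**The case against.** The case against has real weight, and it limits the point in five ways.

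- **The estimator is not stated.** A reader might infer that the plan specifies maximum likelihood with Wald intervals. It does not. Firth and exact conditional regression are logistic regression too, so the remedy is already permitted. What stands is that the unqualified term will normally be run as the software default.
- **Frequency depends on coding.** A reader might infer that infinite odds ratios are common however the marker is coded. The documents do not support that. The lead biomarkers have 1–9 scores and a product of percentages, and numeric terms like these rarely separate. The figures in steps 3 to 5 apply only if markers are dichotomised. Section 13.9 uses that coding for RXR, but only as a descriptive factor.
- **A predictive marker does not always separate more often.** With 8 of 24 patients marker-high, 3 responders and a true odds ratio of 3, the chance is 23%, against 30% for a null marker. The pattern holds for strong effects, not for all.
- **Fisher's test is already planned.** It stays valid with an empty cell, so the p-value for a categorical marker is safe. A reader might also object that it gives no adjusted effect size, but 13.4 names no adjustment covariates, and a one-marker model would not adjust either. What is missing is a method that gives a finite odds ratio and an interval.
- **The gain is modest.** Firth intervals reaching above 1,000 say little more than Fisher's p-value, and the section already calls the work exploratory.

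**Conclusion.** The point holds as a cheap improvement to an exploratory analysis. For a null high/low marker split 12/12 or 8/16, the standard odds ratio does not exist in 22–30% of cases with 3 responders and 4–10% with 5. Averaged over trials that pass stage 1, that is 26–32% at a 12.5% response rate and 10–16% at 20%. For a marker with response rates of 35% versus 5% it is 54% (12/12 split, not conditioned on stage 1).

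These figures rest on dichotomised markers, assumed splits and all 24 patients contributing tissue results. Fewer substudy participants, or a response rate nearer 5%, would generally raise them; numeric scores would lower them greatly. Averages that leave out the stage 1 rule come out higher (34–40% and 13–19%), but they count trials that would have stopped at 9 patients. The primary response analysis and the secondary endpoints do not depend on these models.

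**What to change.** Add to Section 13.4, in the sponsor's own wording, something like:

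> Models of response, and of toxicities with few events, on tumour markers will use Firth-penalised logistic regression with profile penalised-likelihood confidence intervals, one marker per model. IHC scores will enter as numeric terms where possible. Fisher's exact test will be used for categorical markers.

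The cost is one SAP sentence and standard software, with no change to design, sample size or data collection. The downside is that estimates are pulled slightly toward no effect and intervals will be very wide, as step 7 shows. A numeric term also assumes a linear trend in the log-odds across the score. The analyses should still be reported as hypothesis generating.

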13.5 Total Sample Size, Accrual Duration, and Anticipated Time to Study Completion

A maximum of 24 evaluable patients (21 new efatutazone treated patients + 3 already randomized previously) will be accrued onto this randomized phase II study unless the study is closed early for excessive toxicity or lack of efficacy. We anticipate accruing an additional 20% of patients to account for ineligibility, cancellation, major treatment violation, or other reasons. Therefore, maximum accrual is about 30 patients (up to 28 treated with efatutazone (25 new, 3 already enrolled) + 2 placebo treated patients (already enrolled from prior randomized study)). With an expected accrual rate of 1 patient per month, we anticipate that it will take about 3 years to reach full accrual. We anticipate that the study will take approximately 4 years to complete. This allows a 6-month follow-up for the final patient enrolled, along with data entry and analysis.

13.6 AE Stopping Rule

The stopping rule specified below is based on the knowledge available at study development. We note that the Adverse Event Stopping Rule may be adjusted in the event of either (1) the study re-opening to accrual after any temporary suspension or (2) at any time during the conduct of the trial and in consideration of newly acquired information regarding the adverse event profile of the treatment(s) under investigation. The study team may also choose to suspend accrual because of unexpected adverse event profiles that have not crossed the specified rule below.

Accrual will be temporarily suspended to this study if at any time we observe events considered at least possibly related to study treatment (i.e., an adverse event with attribute specified as "possible", "probable", or "definite") that satisfy any of the following criteria:

- If at any time, 3 of the initial 9 treated patients or 33% or more of all patients (i.e. when accrual is greater than 9 patients) have experienced a grade 4 adverse event.
- If at any time, 2 patients have experienced a grade 5 adverse event (not due to progressive disease).

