13.3 Secondary Endpoints

The following endpoints will be assessed: progression-free survival, overall survival, and adverse events. All patients who meet the eligibility criteria, and sign the consent form will be considered evaluable for these endpoints.

Progression-Free Survival: Progression-free survival (PFS) is defined as the time from study entry to the first of either disease progression or death from any cause, where disease progression will be determined based on RECIST 1.1 criteria. PFS will be estimated using the Kaplan-Meier method.

Overall Survival: Overall survival (OS) is defined as the time from study entry to death from any cause. OS will be estimated using the Kaplan-Meier method.

Adverse events: The maximum grade for each type of adverse event will be summarized using CTCAE version 4.0. The frequency and percentage of grade 3+ adverse events will be estimated.

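### The adverse event rule in Section 13.6 can suspend accrual for three grade 4 patients but not when one of the three instead has a related death

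*Combined protocol and SAP*

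**What the plan says.** Section 13.6 opens with a mandatory instruction: "Accrual will be temporarily suspended to this study if at any time we observe events considered at least possibly related to study treatment", followed by two criteria joined by "that satisfy any of the following criteria". Related means an attribution of possible, probable or definite.

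- First criterion: "3 of the initial 9 treated patients or 33% or more of all patients", with the continuation "i.e. when accrual is greater than 9 patients) have experienced a grade 4 adverse event".
- Second criterion: "If at any time, 2 patients have experienced a grade 5 adverse event (not due to progressive disease".

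The section also leaves room for judgement: "The study team may also choose to suspend accrual because of unexpected adverse event profiles that have not crossed the specified rule below". It allows the rule itself to be adjusted after a suspension or when new safety information appears.

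Two other places bear on the reading. Section 13.3 uses cumulative wording when it means a grade or worse: "The frequency and percentage of grade 3+ adverse events will be estimated". Section 13.2 keeps accrual open at the efficacy interim: "The study will remain open during the interim analysis phase due to slow projected accrual rate and minimal expected toxicity".

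**The concern.** A safety trigger should not become harder to reach when an outcome gets worse. Here the grade 4 and grade 5 tallies are kept apart and the first criterion names grade 4 alone. A patient whose only related severe event is fatal therefore adds nothing to the grade 4 tally. If that patient is the only related death, the second criterion is not met either. Replacing one grade 4 patient by a death can then take the trial from mandatory suspension to no mandatory action.

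This matters because Section 13.6 holds the plan's only numeric adverse event boundaries for the trial as a whole, and no planned accrual pause at the interim would catch the case. At stake is whether review is forced or left to discretion in one specific configuration. Alpha, power and sample size for response are not involved.

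**Working it through.** **Inputs from Section 13.6.** Let *g4* be the number of patients counted under the first criterion and *g5* the number with a related grade 5 event not due to progressive disease. The threshold *k(n)* is 3 within the first 9 patients, and afterwards the smallest whole number with k/n ≥ 0.33. The two parts of the first criterion agree where they meet: 3/9 = 33.3%.

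**The rule as written:** suspend if g4 ≥ k(n) or g5 ≥ 2.

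**Step 1: enumerate.** Class each patient by worst related grade, take every state that suspends, and change one grade 4 patient to grade 5.

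| n | k | (k, 0) | (k−1, 1) | (k−2, 2) |
|---|---|---|---|---|
| 9 | 3 | 3,0 suspends | 2,1 does not | 1,2 suspends |
| 12 | 4 | 4,0 suspends | 3,1 does not | 2,2 suspends |
| 18 | 6 | 6,0 suspends | 5,1 does not | 4,2 suspends |
| 24 | 8 | 8,0 suspends | 7,1 does not | 6,2 suspends |

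At n = 24, 8/24 = 33.3% meets the boundary and 7/24 = 29.2% does not. At each sample size checked (9, 10, 12, 15, 18, 21, 24 and 28) exactly one change removes the trigger: from (k, 0) to (k−1, 1).

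**Step 2: size at 9 patients.** The documents give no related grade 4 or grade 5 rates, so the rates p4 and p5 below are assumptions. The pooled rule is g4 + g5 ≥ k or g5 ≥ 2. At n = 9 the two rules differ only in the cell g4 = 2, g5 = 1, so the gap is

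9!/(2!·1!·6!) × p4² × p5 × (1 − p4 − p5)⁶ = 252 × p4² × p5 × (1 − p4 − p5)⁶.

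- 5%/1%: 252 × 0.0025 × 0.01 × 0.94⁶ = 0.0043
- 10%/2%: 252 × 0.01 × 0.02 × 0.88⁶ = 0.0234
- 10%/5%: 252 × 0.01 × 0.05 × 0.85⁶ = 0.0475
- 20%/10%: 252 × 0.04 × 0.10 × 0.70⁶ = 0.1186

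**Step 3: overlap.** Step 2 assumes that no patient who dies also has a separately recorded related grade 4 event, so its gaps are upper bounds. If half of those patients do, the gaps halve. If all do, the gap is zero.

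**Step 4: continuous checking.** The rule applies at any time, so both versions were also run with a check after each patient up to 24, again with mutually exclusive groups.

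| Assumed p4/p5 | By n = 9, as written | By n = 9, pooled | Gap (points) | Gap, 50% overlap | To n = 24, as written | To n = 24, pooled |
|---|---|---|---|---|---|---|
| 5%/1% | 1.2% | 1.6% | 0.4 | 0.2 | 3.3% | 3.7% |
| 10%/2% | 6.6% | 8.9% | 2.3 | 1.2 | 13.9% | 16.1% |
| 10%/5% | 12.2% | 17.0% | 4.8 | 2.4 | 38.3% | 40.9% |
| 20%/10% | 44.8% | 56.7% | 11.9 | 5.9 | 82.2% | 85.5% |

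Over 24 patients the unrounded gaps are 0.4, 2.1, 2.7 and 3.3 points. Except at the lowest rates they are clearly smaller than at 9 patients, because many trials that pass through the gap early meet a trigger later.

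**The case against.** The separate boundaries may be deliberate. Death already has the stricter limit, 2 patients at any sample size, and a second related death triggers whatever the grade 4 count. Only one configuration escapes. A reader could also take grade 4 to mean at least grade 4, and the cumulative wording in Section 13.3 describes a summary of results rather than a trigger. If the patient who died had an earlier recorded related grade 4 event, the existing wording already counts that patient.

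Other provisions soften the gap. The team may suspend for unexpected profiles, and two grade 4 patients plus a related death among nine, where little toxicity is expected, would plausibly qualify. Section 9.3.1 requires 24-hour reporting of serious grade 4 and 5 events, so the situation would be seen. The trigger is itself only a temporary pause. Late in the trial the gap hardly matters: on the sequential model, the chance of reaching 24 patients with 7 grade 4 and 1 grade 5 and no earlier trigger is 0.04% at 10%/2% and 0.6% at 20%/10%. The highest assumed rates fit poorly with the plan's expectation of minimal toxicity.

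Most of this stands as a limit on importance. It does not remove the point. The stricter death limit needs two deaths, so it cannot cover the case of one. Suspension for unexpected profiles is optional, and expedited reporting does not suspend accrual. If at least grade 4 was meant, the text does not say so, and someone applying it literally cannot tell whether a fatal event counts towards the first criterion.

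**Conclusion.** The point holds, as a minor one. On its literal wording the mandatory rule is not monotone in severity: with exactly one related death and the grade 4 tally one short, accrual need not be suspended, although the same number of patients with grade 4 events alone would force it.

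At the lower assumed rates (5%/1% and 10%/2%) the loss in the chance of suspension is 0.4 to 2.3 percentage points within 9 patients and 0.4 to 2.1 points over 24. It reaches 5 to 12 points within 9 patients only at 10%/5% and 20%/10%. All these sizes rest on assumed rates and are upper bounds, since they ignore patients who have both a related grade 4 and a related grade 5 event. The existence of the gap rests on the wording alone, in the case where the death is that patient's only recorded related event of grade 4 or 5.

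**What to change.** In the first criterion of Section 13.6, count patients with a related event of grade 4 or higher, with grade 5 events due to progressive disease excluded as in the second criterion. Keep both thresholds: 3 of the first 9 or 33% thereafter, and 2 grade 5 patients. The state (k−1, 1) then suspends at every sample size, and the rule no longer depends on whether a fatal event also left a separate grade 4 record.

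The cost is a few words and a slightly higher chance of a temporary pause in accrual: about 0.4 points (5%/1%) to 2.1 points (10%/2%) over 24 patients. If the team wants the two tallies kept apart, Section 13.6 should say so and give the reason.

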13.7 Accrual Monitoring Stopping Rule

Given the expected accrual rate is around 1 patient per month, it is expected that the study will take around 3 years to fully accrue. We plan to monitor the accrual continually and if we only end up accruing 3 patients or less in the first year (after study activation), we will consider stopping the trial for slow accrual.

